	
time each day in a consistent manner in relation to food consumption. Morning and evening doses should be administered around the same time within 30 minutes after starting a snack or meal. Patients will gradually titrate their daily dose to the maximally acceptable dose, balancing efficacy and tolerability, or to a maximum number of 12 sprays/day. During the titration phase, there should be an approximately 15-minute interval between sprays.
 
Patients should complete titration within approximately 14 days of their first dose of IMP in each treatment period and should continue at the same dose level achieved at the end of titration phase (i.e., their daily optimized dose) <math>\pm</math> 1 spray/day divided into a morning dose and an evening dose for the remainder of the treatment period.
 
Once a stable daily dose has been reached, patients should gradually decrease the interval between sprays to a target interval of approximately 1 minute between sprays.
 
Throughout each treatment period, patients will be advised to administer IMP at approximately the same time each day in a consistent manner in relation to food consumption.

Control Arm	All patients enrolled in the trial will receive both nabiximols and placebo during the 2-way crossover treatment period.
Procedures	
Assessments/procedures at the trial site include the following:
 

• Informed consent, demographics, previous cannabis use, medical history, electronic diary training, and blood THC test (Visit 1)

• Eligibility check and urine drug screen (including THC) (Visits 1 and 2 [predose])

• Randomization and IMP dosing training (Visit 2 [predose])

• Concomitant medications review, AE review, and vital signs (when at the trial site) measurement (Visits 1 through 10)

• Physical examination (including height measurement at Visit 1 only), 12-lead ECG, and clinical laboratory blood sampling (hematology and biochemistry) (Visits 1, 5, and 9)

• Examination of oral mucosa (Visits 1, 2 [predose], 4, 5, 6 [predose], 8, 9, and 10)

• Body weight measurement (Visits 1, 2 [predose], 6 [predose], and 10)

• Dipstick urinalysis and serum pregnancy test (if appropriate) (Visits 1 and 10)

• Urine pregnancy test (if appropriate) (Visits 2 and 6 [predose])

• PK blood sampling (IMP) at distinct time points (Visits 2, 4, 5, 6, 8, and 9)

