### **9.2.7 Physical Examination**

A full physical examination will be performed at the time points specified in the Schedule of Assessments (see [Appendix 1](#)); height will be recorded at Screening (Visit 1) only.

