**SPONSOR: GW PHARMA LIMITED**

Study Code: GWSP20105  
 EudraCT Number: 2020-003271-18  
 GWSP20105 Protocol V1 22Jul2020

Period	Screening		Treatment Period 1				Treatment Period 2			Safety Follow-up
	Visit Number	Visit 1	Visit 2	Visit 3 (Phone C all)	Visit 4	Visit 5 a	Visit 6	Visit 7 (Phone Call)	Visit 8	
Day/Hour	Day -28 to -1	Day 1 predose	Day 1 2-4 hrs postdose	Day 8 ( $\pm 1$ day)	Day 15 ( $\pm 1$ day)	Day 21 ( $\pm 2$ days)	Day 31 predose ( $\pm 1$ day)	Day 38 ( $\pm 1$ day)	Day 45 ( $\pm 1$ day)	Day 51 ( $\pm 2$ days) End of Treatment Visit
MAS f	X	X	X			X	X			Day 58 (+3 days)
MSSS-88						X				X
T25FW test g		X				X	X			X
C-SSRS	X	X			X	X	X			X
IMP dosing training		X								
IMP dosing h		X				X	X			X
IMP dispensing i		X			X		X		X	
IMP collection and compliance review				X	X	X			X	

AE = adverse events; C-SSRS = Columbia-Suicide Severity Rating Scale; ECG = electrocardiogram; EoT = end of treatment; IMP = investigational medicinal product; MAS = Modified Ashworth Scale; MS = multiple sclerosis; MSSS-88 = Multiple Sclerosis Spasticity Scale; NRS = Numerical Rating Scale; PK = pharmacokinetics; T25FW = Timed 25-Foot Walk; THC =  $\Delta^9$ -tetrahydrocannabinol.

a A washout period of at least 7 days will separate the 2 treatment periods. Following the final dose of IMP in Treatment Period 1, in the morning of Visit 5 (Day 21), patients will discontinue treatment with IMP for the 7 days prior to Visit 6 (Day 31). During the washout period, patients will continue to take their current MS antispasticity medications without any changes in dose.

b A comprehensive physical examination, including an assessment of height, will be completed at Screening (Visit 1) only; subsequent physical examinations will be symptom-directed.

c Serum pregnancy test at Visits 1 and 10; urine pregnancy test at Visits 2 and 6 (predose).

d On the day before PK blood sampling at Visits 4, 5, 8, and 9, patients will be prompted to record whether they started their morning and evening doses of IMP within 30 minutes of a snack or meal. On the day of PK blood sampling, the exact time and date of PK blood sampling and the time of the patient's snacks and meals should be recorded. See Section 9.2.12.1 for the PK blood sampling schedule. Please note that more than one PK sample may be collected at distinct time points during a single visit.

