12.7.5 Physical Examination, ECGs and other Observation Related to Safety

12.7.5.1 Physical Examination: Weight and BMI

Weight is planned to be measured at Screening, Day 1 H0 of each period and at follow-up visit.

Based on the Safety Analysis Set, weight and BMI (as defined in [Section 10.11](#)), observed and change from baseline value at each scheduled timepoint (Period 2 Day 1 H0, Day 21) will be summarized by treatment arm.

Observed and change from Screening to FU will also be summarized by treatment sequence.

The number and percentage of patients meeting a clinically significant change in weight (as defined in [Appendix 6 Abnormality Criteria](#) at any time during within each treatment period will be summarized by treatment arm. All measurements (scheduled or unscheduled) will be used to determine if any abnormality criteria is met (as determined in [Appendix 6 Abnormality Criteria](#)).

Weight and BMI will be listed.

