Appendix 6 Abnormality Criteria

Hepatic abnormality criteria		
Hepatic laboratory Parameters	Abnormality criteria	
ALT	> 3 x ULN	
	> 5 x ULN	
	> 8 x ULN	
	> 10 x ULN	
	> 20 x ULN	
AST	> 3 x ULN	
	> 5 x ULN	
	> 8 x ULN	
	> 10 x ULN	
	> 20 x ULN	
ALP	> 1.5 x ULN	
	> 2 x ULN	
	> 3 x ULN	
Total bilirubin	> 1.5 x ULN	
	> 2 x ULN	
	> 3 x ULN	
	> 5 x ULN	
GGT	> 1 x ULN	
Blood pressures and pulse rate abnormality criteria		
Blood pressures and pulse rate criteria	Abnormality criterion value	Abnormality criterion on change from baseline
SBP	> 180 mmHg	≥ 20 mmHg increase from baseline
	< 90 mmHg	≥ 20 mmHg decrease from baseline
DBP	> 105 mmHg	≥ 15 mmHg increase from baseline
	< 50 mmHg	≥ 15 mmHg decrease from baseline
Pulse rate	> 120 bpm	≥ 10 bpm increase from baseline
	< 50 bpm	≥ 10 bpm decrease from baseline
Weight Abnormality Criteria		
Weight criteria	Abnormality criteria	
Weight (kg)	≥ 7% increase from baseline	
	≥ 7% decrease from baseline	
ECG abnormality criteria		
ECG criteria	Abnormality criteria	

QTcF interval prolongation*	> 450 msec
	> 480 msec
	> 500 msec
Change from baseline in QTcF interval*	> 30 msec increase from baseline
	> 60 msec increase from baseline
PR interval	< 120 msec
	> 200 msec
QRS complex	< 80 msec
	> 120 msec
HR	< 60 bpm
	> 100 bpm

ALT = alanine aminotransferase; AST = aspartate aminotransferase; ALP = alkaline phosphatase; GGT= gamma-glutamyl transferase; SBP = Systolic blood pressure; DBP = diastolic blood pressure; bpm=beats per minutes to be classified as potentially clinically significant, the measurement must satisfy both criteria: the criterion for the value and the criterion for the change relative to baseline.

**Abnormal QTcF interval categories as defined in ICH Guidelines E14*

Any patients fulfilling at least one ECG abnormality criteria (as described in [Appendix 6](#) Abnormality Criteria or having at least one abnormal ECG assessed as significant by the investigator will be listed presenting all his/her ECG information.

Appendix 7 Prohibited medication solely metabolized by UGT1A9 and UGT2B7 and determination criteria

Examples of medications that are solely metabolized by UGT1A9 and UGT2B7 and prohibited for the duration of the trial are provided below.

Medications solely metabolized by UGT1A9		Medications solely metabolized by UGT2B7		
Medication name	ATC code	Medication name	ATC code	Comments
Flavopiridol		Benoxyprofen	M01AE06	
Propofol	N01AX10	Carbamazepine	N03AF01	

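### SAP 12.7.5.1 tabulates Day 21 weight by arm although no weight is scheduled then, and its in-period ≥7% count could credit a Period 1 weight change to the Period 2 arm

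*SAP*

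**What the plan says.** SAP 12.7.5.1 opens by restating the collection schedule: "Weight is planned to be measured at Screening, Day 1 H0 of each period and at follow-up visit". The protocol synopsis, under Procedures, agrees: "Body weight measurement (Visits 1, 2 [predose], 6 [predose], and 10". The protocol's visit lists (9.1.1, 9.1.2.1, 9.1.4.1, 9.1.5) include weight at those four visits. The lists for Visits 4 and 5 (9.1.2.3) and Visits 8 and 9 (9.1.4.3) do not, although Visits 5 and 9 include a physical examination.

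The same SAP section then plans three weight summaries:

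- Weight and BMI by arm: "observed and change from baseline value at each scheduled timepoint (Period 2 Day 1 H0, Day 21) will be summarized by treatment arm".
- A count of patients with a clinically significant weight change "at any time during within each treatment period will be summarized by treatment arm". Appendix 6 sets the threshold at "≥ 7% increase from baseline" or the same decrease. On the data source, the section says "All measurements (scheduled or unscheduled) will be used to determine if any abnormality criteria is met".
- Change from Screening to follow-up, by treatment sequence only.

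**The concern.** Day 21 is called a scheduled weight time point two sentences after a schedule that does not contain it. Anyone programming the table as written would produce a Day 21 row that is empty apart from any unscheduled weights.

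The ≥7% count has a less visible fault. It is meant to compare nabiximols with placebo within each period, but no weight is scheduled while a patient is on treatment. The one scheduled post-exposure weight that falls inside a safety period is taken before the first dose of that period's treatment. The section has no rule saying which arm it belongs to. In a crossover, an attribution error does not merely add noise: it moves the event to the comparator.

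**Working it through.** No power or sample-size arithmetic applies. The check sets the schedule against the SAP's period and baseline definitions.

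**1. Count the scheduled weights for a completer.** There are 4 (Visits 1, 2 pre-dose, 6 pre-dose, 10). Two come after the first dose (Visits 6 and 10). None is taken on treatment: 0 in Period 1 and 0 in Period 2. Column alignment in the schedule grids is hard to follow, so this rests on the written visit lists. The four marks in the weight row of each grid are consistent with them.

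**2. Fill the by-arm table.** It names two time points. Period 2 Day 1 H0 is Visit 6 pre-dose and has scheduled data. Day 21 (Visits 5 and 9) has none.

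**3. Place the weights in the safety periods (SAP 10.1.1).** The lag x is 0 days for anything other than adverse events and C-SSRS.

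| Period | Limits with x = 0 | Scheduled weight after first exposure |
|---|---|---|
| Safety Period 1 | First dose to, at latest, the day before Visit 6 | None |
| Safety Period 2 | Visit 6 (or the IRT call, if earlier) to end of treatment | Visit 6 pre-dose only |
| After Safety Period 2 | – | Visit 10 |

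SAP Table 10.1-1 also files Visit 6 under Period 2, as Day 1.

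**4. Identify what the Visit 6 change measures.** SAP 10.2 defines the clinic-safety baseline as the last value before the first IMP dose and does not reset it for Period 2. The change is therefore Visit 6 pre-dose minus Visit 2 pre-dose. It spans Period 1 treatment and washout, and no Period 2 drug has yet been taken.

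**5. Compare exposure with the arm implied by date.**

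| Sequence | Exposure behind the Visit 6 change | Arm if assigned by date |
|---|---|---|
| Nabiximols/placebo | Nabiximols | Placebo |
| Placebo/nabiximols | Placebo | Nabiximols |

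**6. Check the denominator.** SAP 12.0 bases percentages on the number of patients, or patients at risk, in the arm. Patients with no qualifying weight in the period could then count as having had no event.

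**7. Time from last dose to the weights that do exist,** for patients dosed to the end of the period:

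- Visit 6: nominally 31 − 21 = 10 days. With the Visit 5 (±2) and Visit 6 (±1) windows, the shortest gap is 30 − 23 = 7 and the longest is 32 − 19 = 13.
- Visit 10: 7 (+3) days, so 7 to 10.

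Together the range is 7 to 13 days.

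**8. Compare with other safety data.** Liver elevations in washout go to the Period 1 treatment (SAP 12.7.3.1). Unscheduled C-SSRS in washout goes to the Period 1 arm, and in the by-time-point C-SSRS summary follow-up goes to the last treatment received (12.7.5.3). Weight has no equivalent rule.

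**The case against.** The strongest reply is that this is one stray time point in a descriptive table. Several parts of that reply stand.

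- A reader might infer that the by-arm weight tables have no data. The documents do not support that: Period 2 Day 1 H0 is measured at Visit 6, and unscheduled weights count toward the ≥7% criterion.
- A reader might also infer that the ≥7% count is forced to zero and would be misread as evidence of no weight effect. It is not forced to zero. An unscheduled weight can trigger it, and so can the Visit 6 weight measured against the pre-trial baseline. The problem is which arm receives the event.
- Weight is not named among the secondary safety endpoints, and the protocol lists it separately from physical examination, with different visits. The Visit 10 weight is not lost: it is summarised by sequence, which identifies the Period 2 treatment for completers, and all weights are listed.
- The study was discontinued by a decision of 9 November 2022. The addendum's reporting table names TEAEs, vital signs, labs, ECG and C-SSRS, but not weight, BMI or physical examination. These tables may never be produced.

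The reply does not remove the contradiction within 12.7.5.1 or supply an arm for the Visit 6 weight. Unscheduled weights are not collected systematically and cannot support a comparison between arms.

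Protocol 9.2.7 ("A full physical examination will be performed at the time points specified in the Schedule of Assessments") and Appendix 1 footnote b ("subsequent physical examinations will be symptom-directed") also disagree. That is a separate point about the examination itself and adds nothing to the weight issue.

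**Conclusion.** The point holds as a minor but definite error. One of the two by-arm time points has no scheduled data, each period has 0 scheduled on-treatment weights, and the only scheduled post-exposure weight inside a safety period can be credited to the treatment the patient had not yet received. Followed as written, the rule gives a Day 21 row without scheduled data and an in-period ≥7% count that is either uninformative or potentially reversed.

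This assumes that the visit lists are the operative schedule, that in-period means the SAP's safety periods with x = 0, and that the Visit 6 weight is assigned by date where no other rule is given. The documents give no expected rate of ≥7% change, so the number of patients who could be misattributed cannot be estimated. Practical impact is limited further by early termination and by the addendum's silence on weight. Efficacy is unaffected.

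**What to change.** Amend SAP 12.7.5.1, by addendum if that is the live document, before unblinding:

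1. Delete Day 21 from the by-arm weight and BMI table.
2. Report Visit 6 pre-dose minus Visit 2 pre-dose under the Period 1 arm, and Visit 10 minus Visit 6 pre-dose under the Period 2 arm, each for patients dosed in that period. The second change needs a stated exception to the single pre-trial safety baseline in SAP 10.2.
3. Judge the ≥7% criterion on those two changes plus any unscheduled weights, and use patients with a qualifying weight as the denominator.
4. State in the addendum whether the weight and BMI tables are still produced.

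The cost is wording and a small programming change, using weights already in the schedule. The downside is that the values are off-treatment, about 7 to 13 days after the last dose for patients dosed to the end of the period and longer for those who stopped early, so a short-lived effect could be missed. The tables should carry that footnote. Had data collection still been open, one weighing at Visits 5 and 9, where patients already attend for a physical examination, would have supplied the Day 21 value directly.

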12.7.5.2 Electrocardiogram Results

Based on the safety analysis set, 12-lead ECG parameters (Heart rate (beats/min), PR interval (msec), QRS duration (msec), QT Interval (ms), QTc B Interval (Bazett's formula) (msec), QTcF (Fridericia's formula) Interval (msec) will be summarized by treatment arm. All ECG results will be listed.

ECG results will be summarized for continuous variables and will be presented for the absolute result and change from baseline (Screening) to Day 21.

The number and percentage of patient with any abnormal QTcF (as detailed in [Appendix 6 Abnormality Criteria](#)) values or any other clinically significant ECG abnormality (as defined in [Appendix 6 Abnormality Criteria](#)) at baseline and within each treatment period will be summarized by treatment arm within the Safety Analysis Set.

12.7.5.3 Columbia-Suicide Severity Rating Scale

The Columbia-Suicide Severity Rating Scale is a patient questionnaire that evaluates suicidal ideation and behaviors. In this study, the C-SSRS is assessed at Screening using the "Baseline/Screening Version" and at subsequent timepoints using the "Since Last Visit" version. At the Screening visit, patient eligibility will be assessed with respect to suicidal ideation during the past month and suicidal behavior during the past 5 years.

The C-SSRS questionnaire is planned to be administered by the investigator (or designee) at Screening, Day 1 H0, Day 15 and Day 21 of each treatment period and at FU.

To analyze these questionnaires, events will be considered associated with:

- Nabiximols, if collected between first and last date of nabiximols intake.
- Placebo, if collected between first and last date of placebo intake.
- Any unscheduled C-SSRS questionnaire taken during the wash-out period will be linked to the actual treatment arm defined during Period 1.
- FU if collected after last IMP intake and only the latest one will be used for summary.

Derived parameters are presented in [Section 10.23](#).

On treatment and by timepoints assessments

The number and percentage of patients who have answer "Yes" to each of the 5 suicidal ideation subtypes and each of the 5 suicidal behavior subtypes along with the number and percentage of patients presenting:

- A suicidal ideation,
- A suicidal behavior,
- A suicidal ideation or behavior,
- A self-injurious behaviour without suicidal intent.

will be summarized at baseline, for each scheduled on-treatment timepoint, for the 51-day safety on-treatment period, for last on-treatment assessment and for the Follow-up assessment by treatment arm. For this summary FU assessments will be linked to the last treatment received.

Shift table from baseline to maximal suicidal ideation score as well as a shift table for change in category (no suicidal ideation or behavior, suicidal ideation [without suicidal behavior], suicidal behavior) will also be summarized by treatment arm for patients having a baseline and at least 1 post baseline on-treatment assessment.

The number and percentage of patients presenting a suicide-related treatment-emergent event defined as:

- A treatment emergent suicidal ideation (without suicidal behavior) compared to recent history,
- A treatment emergent serious suicidal ideation compared to recent history,
- An emergence of serious suicidal ideation compared to recent history,
- An emergence of suicidal behavior compared to all prior history,

will be summarized by treatment arm.

Observed scores and changes from baseline in Suicidal ideation score and in Suicidal intensity rating score will be summarized at baseline and for each scheduled on-treatment timepoint, for the last on-treatment assessment and for the worst on-treatment score and for the follow-up assessment, by treatment arm using n, mean, median, SD, Q1, Q3, min and max.

Cumulative distribution function on change from baseline to last on-treatment value will be plotted by treatment arm. This will be displayed as an increasing CDF.

Withdrawal assessment from last on-treatment visit

- The number and percentage of patients presenting:
- An emergence of suicidal ideation without suicidal behavior,
- An emergence of serious suicidal ideation,
- An emergence of suicidal behaviour.

From last on treatment assessment to FU will be summarized by treatment arm according to last treatment received.

Observed at last on-treatment assessment and FU along with change from last on-treatment assessment in Suicidal intensity rating score will be summarized by treatment group using n, mean, median, SD, Q1, Q3, min and max. A shift table of from last on-treatment to FU score will also be displayed.

For patients with any post-baseline suicidal ideation or suicidal behavior, listings will be prepared including all C-SSRS scores for these patients.

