Patients who complete the 2 treatment periods will complete an End of Treatment Visit (Visit 9). Patients who discontinue IMP early will be encouraged to remain in the study for the duration of the treatment period in which they discontinue IMP and will complete an End of Treatment Visit (Visit 9) at the end of that period. A Safety Follow-up Visit (Visit 10) will occur 7 (+ 3) days after the last dose of IMP or after the End of Treatment visit (Visit 9), whichever is later, for all patients.

A schematic ([Figure 1-1](#)), presented at the end of [Section 1](#), depicts the overall trial design. More detailed information on treatment and trial procedures is provided in [Section 8](#) and [Section 9](#), respectively.

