### **9.1.5 Safety Follow-up Visit (Visit 10 [Day 58])**

The Safety Follow-up Visit will occur 7 days after the last dose of IMP or after the End of Treatment visit (Visit 9), whichever is later. A visit window of + 3 days from the

scheduled visit date is permitted, but it is preferred that the visit is performed on the scheduled visit day, where possible.

The following assessments/procedures will be performed:

- Concomitant medication review
- AE review
- Examination of oral mucosa
- Body weight measurement
- Vital signs measurement
- Dipstick urinalysis
- Serum pregnancy test (if appropriate)
- C-SSRS assessment

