### **9.2.15.3 Columbia-Suicide Severity Rating Scale**

The definitions of behavioral suicidal events used in this scale are based on those used in the Columbia Suicide History Form. Questions are asked on suicidal behavior, suicidal ideation, and intensity of ideation. At Screening (Visit 1), questions will be in relation to lifetime experiences (baseline). Questioning at all subsequent visits will be in relation to the last assessment (since last visit).

The C-SSRS is to be administered by the investigator or his or her qualified designee at Visits 1 through 10 as indicated in the schedule of assessments (see [Appendix 1](#)); “qualified designee” is defined as anyone who has completed the C-SSRS training within the past 2 years or has continually administered C-SSRS assessments throughout the trial since obtaining the training certificate. The survey should be completed by the same assessor, where possible, throughout the trial. Assessments will be conducted only if patients are capable of understanding and answering the questions, in the investigator’s opinion.

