## **10 WITHDRAWAL**

In accordance with the Declaration of Helsinki, the ICH Tripartite Guideline for GCP Topic E6(R2), the US Food and Drug Administration (FDA) regulations relating to GCP and clinical trials, the EU Clinical Trials Directive, the EU GCP Directive, and/or other applicable regulations, a patient has the right to withdraw from the study at any time and for any reason, with no obligation to provide a reason, and without prejudice to his or her future medical care by the physician or at the institution.

The patient must be withdrawn from the trial if any of the following apply:

- Administrative decision by the investigator, GW, or a regulatory authority
- Withdrawal of patient consent
- Lost to follow-up

The patient must cease IMP and should remain in the trial if any of the following apply:

- Pregnancy
- Protocol deviation that is considered to potentially compromise the safety of the patient
- Suicidal behavior or ideation of type 4 or 5 during the treatment period, as evaluated with the C-SSRS
- ALT or AST  $> 3 \times$  ULN with the appearance of fatigue, nausea, vomiting, right upper quadrant pain or tenderness, fever, rash, and/or eosinophilia ( $> 5\%$ )
- ALT or AST  $> 5 \times$  ULN
- ALT or AST  $> 3 \times$  ULN **and** (total bilirubin [TBL]  $> 2 \times$  ULN **or** international normalized ratio [INR]  $> 1.5$ )

The patient may be required to cease IMP at the discretion of the investigator and should remain in the trial for any of the following reasons:

- Did not meet eligibility criteria
- Patient noncompliance
- AE (including clinically significant laboratory result) that, in the opinion of the investigator, would compromise the continued safe participation of the patient in the trial
- Any evidence of drug abuse or diversion
- Disease progression (defined as a relapse of MS requiring a change in treatment)

Should a patient request or decide to withdraw from the study, all efforts must be made to complete and report the observations as thoroughly as possible up to the date of withdrawal. Patients withdrawing due to an AE should be followed up according to [Section 12.7](#). All information should be reported on the applicable eCRF pages (refer to [Section 9.2](#)). A Safety Follow-up Visit should take place 7 (+ 3) days after last dose of IMP or after the End of

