10.0 Conventions and Derivations

10.1 Study Period, Reference Day, Study Day, Analysis Day and Visit Window

10.1.1 Study Periods

For each patient, there will be a screening period, an evaluable period composed of a treatment period 1, a washout period, and a treatment period 2, and a safety follow-up period.

The Screening period starts on the day of the informed consent signature and ends on Day 1 (as defined on in [Section 10.1.2](#)) before 1st IMP intake.

The evaluable period starts on the day of randomization and ends the day of the safety follow-up visit.

- The **51-day efficacy period** which starts on the first day of IMP administration and ends at the end of treatment date.
 - This period will be composed of:
 - The **21-day on-treatment efficacy Period 1** which starts the day of first IMP intake during Period 1 and ends the earliest between end of Period 1 Day 21 date and permanent end of treatment date;
 - The on-treatment **wash-out period** which begins the day following the end of the 21-day on-treatment efficacy Period 1 and ends the day before the beginning of the 21-day on-treatment efficacy Period 2;
 - The **21-days on-treatment efficacy Period 2** which starts the day of IRT call for Period 2 and ends on the end of treatment date. This period is only defined for patients exposed to IMP during Period 2.
 - It will be used for efficacy analyses using the Full Analysis Set.
- The **51-day safety period** which starts on the first day of IMP administration and ends at the end of treatment date (+ x days).
 - This period will be composed of:
 - The **21 day on-treatment Safety Period 1** which starts the day of first IMP intake during Period 1 and ends the earliest between end of the wash out period date, the day before the date of IRT call for Period 2, the day before Visit 6 date and permanent end of treatment date + x days.
 - The **21 day on-treatment Safety Period 2** which starts the earliest between date of Visit 6, day of IRT on treatment safety period call for Period 2 date, and ends on the end of treatment day date + x days.
 - x will be equal to 14 days for Adverse events, 4 days for C-SSRS and 0 days otherwise.
 - it will be used for safety analyses using the Safety Analysis Set (unless otherwise specified).
- The **Follow-up period** which starts the day following the 51-day on-treatment safety period and ends on the end of study date.

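### SAP 12.7.5.3 summarises only the latest C-SSRS form after the last dose, so earlier off-drug reports from early stoppers who stay in the trial are left out of the follow-up tables

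*SAP*

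**What the plan says.** SAP 12.7.5.3 ties a form to a treatment by its collection date. A form belongs to "Nabiximols, if collected between first and last date of nabiximols intake", with matching wording for placebo. A form is "FU if collected after last IMP intake and only the latest one will be used for summary".

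The schedule in the same section places the questionnaire "at Screening, Day 1 H0, Day 15 and Day 21 of each treatment period and at FU". Protocol 9.2.15.3 fixes the recall period of every form after screening: "Questioning at all subsequent visits will be in relation to the last assessment (since last visit". SAP 12.7.5.3 likewise names the since-last-visit version for these time points.

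Off-drug visits are part of the design. Protocol 4.1 states: "Patients who discontinue IMP early will be encouraged to remain in the study for the duration of the treatment period in which they discontinue IMP". Protocol 10 lists among the reasons to cease IMP while remaining in the trial: "Suicidal behavior or ideation of type 4 or 5 during the treatment period, as evaluated with the C-SSRS".

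SAP 10.1.1 sets a different on-treatment limit, adding x days to the end-of-treatment date: "x will be equal to 14 days for Adverse events, 4 days for C-SSRS and 0 days otherwise".

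After the early termination, the SAP addendum's reporting table appears to keep C-SSRS reporting as the SAP has it. The table's layout is broken in the text available, but that is its natural reading.

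**The concern.** Since-last-visit forms cover consecutive, non-overlapping stretches of time. Keeping only the last of several is not a summary of the off-drug time; it is a summary of its final stretch. For on-treatment time the SAP does report a worst score as well as the last one. For off-drug time it reports only the latest, and gives no reason.

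The patients with more than one off-drug form are those who stopped early and stayed, and some of them may have stopped for tolerability or psychiatric reasons. Leaving out forms can only lower the counts in the follow-up table and in the comparison of the last on-treatment visit with follow-up. In a table that may hold few events, one omitted type 4 or 5 report would change what a reader sees.

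**Working it through.** The plan gives no figure to reproduce. The check counts scheduled forms and then traces two cases.

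**Inputs.** Post-baseline forms fall nominally on Day 15 and Day 21 of a period (SAP 12.7.5.3) and at follow-up on Day 28, counted from the start of the period in which IMP is stopped for good (SAP 10.1.3, Table 10.1-1). The patient is assumed to stay in the trial and attend on the nominal days; visit windows would move the boundaries by a day or two.

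**Formula.** Let d be the day of the last dose, and let w be 0 under SAP 12.7.5.3 or 4 under SAP 10.1.1.

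- Off-drug forms = number of days in {15, 21, 28} greater than d + w.
- Forms left out = off-drug forms minus 1, because only the latest is used.

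| Rule | Last dose on day | Off-drug forms | Used | Left out |
|---|---|---|---|---|
| 12.7.5.3 (w = 0) | 1-14 | 3 | 1 | 2 |
| 12.7.5.3 (w = 0) | 15-20 | 2 | 1 | 1 |
| 12.7.5.3 (w = 0) | 21 | 1 | 1 | 0 |
| 10.1.1 (w = 4) | 1-10 | 3 | 1 | 2 |
| 10.1.1 (w = 4) | 11-16 | 2 | 1 | 1 |
| 10.1.1 (w = 4) | 17-21 | 1 | 1 | 0 |

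**Time covered.** For a last dose on Day 5, off-drug time to nominal follow-up is 28 - 5 = 23 days. The one form used covers 28 - 21 = 7 of them, leaving 23 - 7 = 16 days outside the follow-up summary.

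**Where the two sections disagree.** They classify a form differently when it is taken 1 to 4 days after the last dose. That is the Day 15 form for a last dose on Day 11-14, and the Day 21 form for a last dose on Day 17-20.

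**Case 1: last dose on Day 16.** Suppose the Day 15 form shows no ideation, the Day 21 form type 4 ideation, and the follow-up form none. The Day 21 form is 21 - 16 = 5 days after the last dose, so it is off treatment under either rule, and it is not the latest form. The follow-up table shows no ideation, and the change from the last on-treatment visit to follow-up is zero. The type 4 report is in neither.

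**Case 2: last dose on Day 6 of Period 1.** The Day 1 form is pre-dose and the next is due on Day 15, so there is no scheduled on-treatment form even with 4 days added (6 + 4 = 10). The comparison of last on-treatment visit with follow-up then has no starting value. SAP 10.23 rules out imputation, so the result is missing; it is not a recorded absence of emergence. A type 4 report at Day 15 would still be left out of the follow-up table.

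**The case against.** A reader might infer that such events vanish from everything but the listings. The documents do not support that.

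- Suicidal ideation and behavior is a pre-specified adverse event of special interest (SAP Appendix 11), tabulated by arm (12.7.2.3), with an adverse-event window of 14 days after the last dose (10.1.1). The Day 15 report in Case 2 comes 15 - 6 = 9 days after the last dose, and the Day 21 report in Case 1 comes 5 days after. Either could be counted there. This stands, but only if the investigator also records an adverse event.
- SAP 10.23 defines emergent suicidal behavior as an occurrence after baseline, with no on-treatment or latest-form limit, and its increase-from-baseline definitions for ideation state no end of window. These may capture some off-drug reports. For ideation, however, 10.23 gives a separate line for the change to the follow-up visit, which suggests that the first line is meant for on-treatment forms.
- SAP 10.1.3 prefers on-treatment to off-treatment safety assessments within a visit window, which implies that off-treatment forms might be eligible for Day 15 or Day 21. But 12.7.5.3 tabulates scheduled on-treatment time points, and the SAP does not say which rule prevails.

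A reader might also infer that the rule hides the very events that led to stopping under Protocol 10. It does not do so in general: the triggering event precedes the stop and, if its form is dated on or before the last dose, it is in the on-treatment tables. Later, separate reports are what can be missed.

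Finally, a worst-over-all-forms summary is not neutral. Early stoppers have more off-drug forms and longer off-drug observation than completers, whose only scheduled off-drug form is Visit 10. This is a good reason to add such a row beside the latest value and not to replace it.

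**Conclusion.** The point holds for patients who stop IMP early and remain in the trial, and for anyone with additional unscheduled off-drug forms. Followed as written, SAP 12.7.5.3 leaves up to two scheduled off-drug forms per such patient out of the follow-up table and the last-on-treatment-to-follow-up comparison. The 4-day extension in 10.1.1 narrows the loss but does not remove it. The disagreement between the two sections needs resolving in any case, because the same form could be programmed either way. A patient who completes both periods loses no scheduled form, and the listings give all C-SSRS scores for any patient with post-baseline ideation or behavior.

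It is tempting to multiply the per-patient loss by the planned 190 patients and a guessed stopping rate. The documents do not support such a total: they give no early-stopping rate, staying in the trial is only encouraged, and the addendum says that recruitment ended short of plan without stating the final number. The point rests on the per-patient count and on nominal visit days.

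**What to change.** 1. State one on-treatment limit for C-SSRS and use it in both SAP 10.1.1 and 12.7.5.3.
2. Keep the latest follow-up value. Beside it, add a row for the worst response (any Yes) over all forms after that limit, by last treatment received.
3. Define emergence after treatment as an increase on any later form. Where no on-treatment form exists, use the pre-dose baseline as the comparator.
4. With the added row, show the number of off-drug forms or the off-drug observation time per arm, so that the unequal follow-up of early stoppers and completers is visible.
5. Say whether the baseline-referenced definitions in 10.23 include off-drug forms, and whether 10.1.3 or 12.7.5.3 governs off-drug forms that fall in the Day 15 and Day 21 windows.

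The cost is SAP or addendum wording plus one programming rule (maximum as well as last). No new data are needed.
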